#### 6.4.3.3 Local laboratory values

Box plots of local laboratory values will be generated for baseline values and for values measured during the course of the study by treatment group and visit. Each box plot will show the first quartile, the median, and the third quartile. Outliers (values outside the box plot) will also be plotted. If appropriate, horizontal lines representing boundaries for abnormal values will be plotted.

For each local laboratory measure, summary statistics will be presented by treatment group and timepoint, as well as changes from baseline for postenrollment values. In addition, the number (percentage) of participants with local laboratory values recorded as meeting Grade 1 AE criteria or above as specified in the DAIDS AE Grading Table (Section 11.2.2) will be tabulated by treatment group for each postvaccination timepoint. Reportable clinical laboratory abnormalities without an associated clinical diagnosis will also be included in the tabulation of AEs described above.

#### 6.4.3.4 Reasons for vaccination discontinuation and early study termination

The number and percentage of participants who discontinue vaccination and who terminate the study early will be tabulated by reason and treatment group.

### 6.4.4 Immunogenicity analysis

#### 6.4.4.1 General approach

For the statistical analysis of immunogenicity endpoints, data from enrolled participants will be used according to the initial randomization assignment. Assay results that are unreliable, from specimens collected outside of the visit window, or from HIV-infected participants postinfection are excluded. Since the exact date of HIV infection is unknown, any assay data from blood draws 4 weeks prior to an infected participant's last seronegative sample and thereafter may be excluded. If an HIV-infected participant does not have a seronegative sample postenrollment, then all data from that participant may be excluded from the analysis.

Discrete categorical assay endpoints (eg, response rates) will be analyzed by tabulating the frequency of positive response for each assay by antigen and treatment group at each timepoint for which an assessment is performed. Response rates will be presented with their corresponding 95% confidence interval estimates calculated using the score test method [31].

To compare the response rates of any 2 groups, a significant difference will be declared if the 2-sided p-value from either a (stratified when appropriate) Barnard's or Fisher's exact test is  $\leq 0.05$ . To compare the response rates among more than 2 groups, first an overall test for any difference in response rate among all groups will be conducted, using a Freeman-Halton exact test (or a Chi-square test, depending on whether there are numbers less than 5 in a given cell of the contingency table). When all pair-wise comparisons between the multiple vaccine groups are of interest, a Tukey-like procedure for proportions as described in [32] will be used. Parametric regression models may also be used to adjust for covariates of interest. More details will be provided in the SAP.

For quantitative assay data (eg, IC50 titer from the neutralizing assay), graphical and tabular summaries of the distributions by antigen, treatment group, and timepoint will be made. For all primary and secondary immunogenicity endpoints, box plots and plots of estimated reverse cumulative distribution curves will be used for graphical display of all of the study groups. Typically the results will be shown for each vaccine group and for the combined groups.

To compare the response magnitude at a specific time-point between any 2 groups, a nonparametric (stratified, if appropriate) Wilcoxon rank sum test will be used if the data are not normally distributed and with a (stratified, if appropriate) 2-sample t-test if the data appear to be normally distributed. To test for magnitude differences at a specific time-point among more than 2 groups, first a Kruskal-Wallis rank test or an F-test (depending on the normality assumption) will be used to test for overall differences. Secondly, if the overall test is significant at the 2-sided 0.05 level, then individual tests comparing pairs of vaccine groups will be done unless pre-specified. When all pair-wise comparisons between the multiple vaccine groups are of interest, the Tukey procedure [32] will be used. Parametric regression models may also be used to adjust for covariates of interest. More details will be provided in the SAP. An appropriate data transformation (eg, log10 transformation) may be applied to better satisfy assumptions of symmetry and homoscedasticity.

More sophisticated analyses employing repeated measures methodology (eg, linear mixed models or marginal mean models fit by generalized estimating equations) may be utilized to incorporate immune responses over several timepoints and to test for differences over time. However, inference from such analyses would be limited by the small sample size of this study. All statistical tests will be 2-sided and will be considered statistically significant if  $p \leq 0.05$ .

Based upon previous HVTN trials, missing 10% of immunogenicity results for a specific assay is common due to study participants terminating from the study early, problems in shipping specimens, or low cell viability of processed PBMCs. To achieve unbiased statistical estimation and inferences with standard methods applied in a complete-case manner (only including participants with observed data in the analysis), missing data need to be missing completely at random (MCAR). Following the most commonly used definition, MCAR assumes that the probability of an observation being missing does not depend on any participant characteristics (observed or unobserved). When missing data are minimal (specifically if no more than 20% of participants are missing any values), then standard complete-case methods will be used, because violations of the MCAR assumption will have little impact on the estimates and hypothesis tests.

If a substantial amount of immunogenicity data are missing for an endpoint (at least 1 value missing from more than 20% of participants), then using the methods that require the MCAR assumption may give misleading results. In this situation, analyses of the immunogenicity endpoints at a specific timepoint will be performed using parametric generalized linear models fit by maximum likelihood. These methods provide unbiased estimation and inferences under the parametric modeling assumptions and the assumption that the missing data are missing at random (MAR). MAR assumes that the probability of an observation being missing may depend upon the observed responses and upon observed covariates, but not upon any unobserved factors. Generalized linear models for response rates will use a binomial error distribution and for quantitative endpoints, a normal error distribution. For assessing repeated immunogenicity measurement, linear mixed effects models will be used. If the immunological outcomes are left- and/or right-

censored, then the linear mixed effects models of Hughes [33] will be used, because they accommodate the censoring. In addition, secondary analyses of repeated immunogenicity measurements may be done using weighted generalized estimating equation [34] methods, which are valid under MAR. All of the models described above in this paragraph will include as covariates all available baseline predictors of the missing outcomes.

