## 6 Statistical considerations

### 6.1 Accrual and sample size calculations

Recruitment will target enrolling 100 healthy, HIV-uninfected participants previously enrolled into HVTN 205. Eligible participants will be assigned into one of 5 study groups (20 in each group) depending on their previous vaccine regimen received in HVTN 205. Participants previously vaccinated with DDMM will be randomized to receive MVA/HIV62B alone, AIDSVAX B/E alone, or a combination of MVA/HIV62B and AIDSVAX B/E given concurrently. HVTN 205 participants initially vaccinated with MMM will be randomized to be boosted with MVA/HIV62B alone or a combination of MVA/HIV62B and AIDSVAX B/E given concurrently.

Since enrollment is concurrent with receiving the first study vaccination, all participants will provide some safety data. However, for immunogenicity analyses, it is possible that data may be missing for various reasons, such as participants terminating from the study early, problems in shipping specimens, low cell viability of processed peripheral blood mononuclear cells (PBMCs), or high background. Immunogenicity data from 17 phase 1 and 2 phase 2a HVTN vaccine trials, which began enrolling after June 2005 (data as of September 2014), indicate that 10% is a reasonable estimate for the rate of missing data. For this reason, the sample size calculations in Section 6.1.2 account for 10% enrolled participants having missing data for the primary immunogenicity endpoints. To maximize the power of evaluating boosting regimens, Groups 1 and 3 with MVA/HIV62B-only boost and Groups 2 and 4 with MVA/HIV62B + AIDSVAX B/E boost will be combined in the primary analyses accounting for the prior priming regimens, in addition to analyses by each individual group. Interaction tests will be used to evaluate whether the effect of boosting regimens differs by the prior prime regimens. However, the study has low power to detect the interaction; therefore we will treat these interaction analyses as exploratory.

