### 6.1.2 Sample size calculations for immunogenicity

The main goals of this trial regarding immunogenicity outcomes involve a preliminary estimation of Ab response rates and magnitudes among participants who received MVA/HIV62B and AIDSVAX B/E alone or together as boost after prolonged immunologic rest. No adjustment for multiple comparisons will be made for the use of multiple assays. The precision with which the true response rate can be estimated from the observed data depends on the true underlying response rate and the sample size. Two-sided 95% confidence intervals for the response rate based on observing a particular rate of responses in the vaccinees is shown in Table 6-3. Calculations are done using the score test method [31]. The n = 18 and 36 assume a 10% loss of data.

**Table 6-3 Two-sided 95% confidence intervals for the true response rate based on observing a particular rate of responses in the individual (n=18) or combined groups (n = 36)**

| No. of responses | Observed response rate (%) | CI           |
|------------------|----------------------------|--------------|
| n = 18           |                            |              |
| 1/18             | 5.6                        | [1, 25.8]    |
| 3/18             | 16.7                       | [5.8, 39.2]  |
| 5/18             | 27.8                       | [12.5, 50.9] |
| 7/18             | 38.9                       | [20.3, 61.4] |
| 9/18             | 50                         | [29, 71]     |
| 11/18            | 61.1                       | [38.6, 79.7] |
| 13/18            | 72.2                       | [49.1, 87.5] |
| 15/18            | 83.3                       | [60.8, 94.2] |
| 17/18            | 94.4                       | [74.2, 99]   |
| n = 36           |                            |              |
| 3/36             | 8.3                        | [2.9, 21.8]  |
| 5/36             | 13.9                       | [6.1, 28.7]  |
| 7/36             | 19.4                       | [9.8, 35]    |
| 11/36            | 30.6                       | [18, 46.9]   |
| 15/36            | 41.7                       | [27.1, 57.8] |
| 19/36            | 52.8                       | [37, 68]     |
| 23/36            | 63.9                       | [47.6, 77.5] |
| 27/36            | 75                         | [58.9, 86.2] |
| 33/36            | 91.7                       | [78.2, 97.1] |

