**Table 6-4 Power for comparison of response rates between 2 groups (n1 = 18 and n2 = 18 or n1=36 and n2=36)**

| True response rate Group 1 (%) | Minimum true response rate in Group 2 in order to detect a difference |           |
|--------------------------------|---|-----------|
|                                | 80% power   | 90% power |
|                                | n1 = 18, n2 = 18  |           |
| 10                             | 58  | 65        |
| 20                             | 71  | 77        |
| 30                             | 81  | 87        |
| 40                             | 89  | 94        |
| 50                             | 95  | 99        |
| 60                             | 100   | -         |
|                                | n1 = 36, n2 = 36  |           |
| 10                             | 41  | 46        |
| 20                             | 54  | 60        |
| 30                             | 66  | 71        |
| 40                             | 75  | 80        |
| 50                             | 84  | 87        |
| 60                             | 91  | 94        |
| 70                             | 97  | 99        |

Table 6-5 shows the power for comparison of immune response magnitudes between 2 groups for detecting a range of effect sizes. Effect size is the difference of means per one unit of standard deviation (sd). A two-sided two-sample t test is used to compare immune responses between two groups assuming equal variances at significance level of 0.05. The actual difference in group means depends on the standard deviation. For example, the power of detecting effect size of 1 between 2 groups of size 18 is 83%. The actual difference of group means corresponding to this effect size will depend on the variation of the endpoints. The larger the variation, the larger difference of group means can be detected. So for assay with smaller variation  $sd = 0.2$ , there is 83% power to detect 0.2 difference in group means, while for assay with larger variation  $sd = 1.1$ , the same 83% power can only detect 1.1 difference in group means. For the primary immunogenicity endpoints, binding Ab and neutralizing Ab data,  $\log_{10}$  transformation will be done before statistical testing. The HVTN 205 data indicate that the standard deviations of  $\log_{10}$  IC50 titer, IgG and IgA binding Ab magnitudes from vaccinee groups range from 0.1 to 1.2 depending on antigens.

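### The above-20% missing-data model at Day 126 lacks the MAR validity the plan claims for it, and the statement that MCAR violations matter little at up to 20% missing is unsupported

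*Combined protocol and SAP*

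**What the plan says.** Section 6.4.4.1 states that complete-case methods need data missing completely at random (MCAR). It then uses them whenever no more than 20% of participants are missing any values, because "violations of the MCAR assumption will have little impact on the estimates and hypothesis tests". No figure or citation supports this, and the 20% is not applied by group.

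Above 20%, "analyses of the immunogenicity endpoints at a specific timepoint will be performed using parametric generalized linear models fit by maximum likelihood". These models are said to be unbiased under the parametric model and MAR, and "MAR assumes that the probability of an observation being missing may depend upon the observed responses and upon observed covariates". The covariates are the available baseline predictors of the missing outcome. Linear mixed models, in a censored version where needed, are planned for assessing repeated measurements, with weighted GEE as an optional secondary analysis.

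The primary antibody endpoints in Section 5.1 are set 2 weeks after each boost, which Section 10.3 places at Days 14 and 126. On expected loss, Section 6.1 cites earlier network trials that "indicate that 10% is a reasonable estimate for the rate of missing data", and Section 6.4.4.1 says "missing 10% of immunogenicity results for a specific assay is common".

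**The concern.** Two statements in the section do not follow from the methods it names.

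First, the stated MAR condition lets Day 126 missingness depend on the Day 14 response. A GLM fitted to Day 126 alone, with baseline covariates only, cannot use that response. When loss follows Day 14, the plan's condition is met but its conclusion is not.

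Second, the complete-case clause is unconditional, yet the plan has just said that these methods require MCAR. The 20% is pooled over five groups, so it does not limit the imbalance between the two arms in any one comparison.

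At stake is the Day 126 comparison of boost regimens, which is half of the primary immunogenicity timepoints. Some arms receive two active products and others one, and Section 4.8 says the combination is untested in humans, so arm-differential loss cannot be ruled out in advance.

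**Working it through.** **Inputs from the documents.** Total enrolment: "Recruitment will target enrolling 100 healthy, HIV-uninfected participants previously enrolled into HVTN 205", in five groups of 20. Expected loss is 10%, so "The n = 18 and 36 assume a 10% loss of data". Test: "A two-sided two-sample t test is used to compare immune responses between two groups assuming equal variances at significance level of 0.05". The missingness mechanisms and the correlations between visits are not in the documents. Those below are assumptions.

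**The plan's own figure.** Two groups of 18, effect size 1: noncentrality = 1 x sqrt(18/2) = 3 on 34 degrees of freedom. Power is 83.0%, against 83% in Table 6-5. It reproduces, so the planning figures are not at issue. At the 20% limit (n = 16 per group) it is 78.1%.

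**Step 1: what the Day 126 GLM uses.** Write Y14 and Y126 for the responses and X for arm and baseline covariates. The GLM likelihood is the product of f(Y126 | X) over participants with Y126 observed. Someone with Y14 but no Y126 contributes a factor of 1. The fit is therefore a covariate-adjusted complete-case analysis, valid if P(missing | X, Y14, Y126) = P(missing | X). The joint likelihood f(Y14 | X) x f(Y126 | Y14, X) keeps that person's first factor and is valid when P(missing) depends on X and Y14, which is the condition the plan states. At Day 14 the observed history is baseline only, so the claim can hold there.

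**Step 2: complete-case bias within an arm.** Bias = fraction missing x (observed mean - missing mean). At 20% missing, a gap of 0.5 SD gives 0.2 x 0.5 = 0.10 SD, and 1 SD gives 0.2 x 1 = 0.20 SD. The between-arm bias is the difference of these quantities. It cancels when the arms match and remains when they do not. For a response rate, 8 responders among 16 observed of 20 (50%) is compatible with 8/20 = 40% to 12/20 = 60%.

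**Step 3: how uneven the loss may be.** Two combined arms of 40 losing 10% and 30% lose 4 + 12 = 16. If Group 5 loses 4 of 20, the total is 20 of 100, still inside the complete-case rule.

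**Step 4: simulation under no true difference.** 40 per arm; correlations Day 0/Day 14 0.5, Day 0/Day 126 0.4, Day 14/Day 126 0.7. Low Day 14 responders are more likely to be missing at Day 126 (logistic slope 1.5 per SD). The contrast is the lower-loss arm minus the higher-loss arm. Results move by about 0.01 SD between runs.

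| Loss by arm | Complete case: bias, type I error | Baseline-covariate GLM | Using Day 14 |
|---|---|---|---|
| 20% and 20%, same mechanism | 0.00 SD, 5% | about 0, 5% | about 0, 5% |
| 5% and 15% (Day 14-driven in both arms, or in one only) | about -0.08 to -0.12 SD, 6-8% | about -0.06 to -0.09 SD, 6-7% | about 0, 5% |
| 10% and 30% (Day 14-driven in one arm) | -0.23 SD, 15% | -0.17 SD, 11% | 0.00 SD, 5% |

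The plan would not use the GLM in the second row, where overall loss is 10%; it is shown for comparison.

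A second mechanism lies inside the above-20% branch: 25% missing overall, 40 per arm, with loss in one arm of 50% below and 5% above the Day 14 mean, and a flat 22.5% in the other. At Day 14/Day 126 correlations of 0.3, 0.6 and 0.8 the GLM bias is -0.06, -0.14 and -0.18 SD, with type I error 5.7%, 8.5% and 11.4%. The joint likelihood stays at about 0 and 4-5%.

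**Step 5: separation in the binomial GLM.** Section 4.8.1.2 reports gp41 response rates of 93% and 98% in HVTN 205. P(all respond) = rate^n: 0.93^18 = 27%, 0.98^18 = 70%, 0.93^36 = 7%, 0.98^36 = 48%. When one arm is all responders and the other is not, the ordinary arm estimate is not finite, and no fallback is stated.

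**Step 6: the counting unit.** The section does not say whether a missing value is counted at one visit or across visits. With 10% loss counted per endpoint and timepoint, P(more than 20 of 100) = 0.08%. If both primary visits are pooled with independent loss, the per-person rate is 1 - 0.9^2 = 19% and the probability is 34%. It falls to 16%, 5% and 0.9% at missingness correlations of 0.25, 0.5 and 0.75.

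**The case against.** The rule is written in advance and depends on the amount of missing data, not on results. The baseline covariates make the GLM valid for covariate-dependent loss. Mixed models are already planned for repeated measurements. Participants and site staff are blinded (Section 6.3), and unblinded immunogenicity analysis waits until everyone has completed the visit (Section 6.4.5.2), so loss driven directly by antibody level is unlikely. Those who stop vaccination are urged to stay in follow-up (Section 7.3.3). The worst simulated setting has twice the planned loss and a one-arm mechanism. The immunogenicity aim is preliminary estimation (Section 6.1.2).

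Most of this stands and limits the size of the problem. It does not rescue the two statements. The mixed models are assigned to repeated-measures assessment, while the primary comparisons are timepoint-specific and so go to the GLM.

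A reader might infer that the method switches by chance, or that the primary test is not fixed in advance. The documents do not support this. Section 6.4.4.1 frames the rule for an endpoint and the GLM for a specific timepoint, and on that reading a switch at 10% loss has probability 0.08%. The 34% needs both visits pooled and independent loss, although early termination, the first cause the section lists, makes losses within a person correlate. Counting baseline as a further independent loss is not plausible, since enrolment coincides with first vaccination and specimens should be taken before it. What remains is an unstated counting unit.

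**Conclusion.** The point holds for two statements in Section 6.4.4.1. The MAR property claimed for the single-timepoint GLM fails at Day 126 whenever missingness depends on Day 14 beyond the baseline covariates; this follows from the likelihood and needs no simulation. The complete-case clause is unsupported and is untrue when loss or its mechanism differs by arm.

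The size depends on mechanisms the documents do not give. It is negligible with equal loss and mechanism, small at the planned 10% overall (about -0.08 to -0.12 SD and 6-8% type I error for complete case at 5% versus 15%), and material at the 20% limit with 10% versus 30% (-0.23 SD and 15% for complete case; -0.17 SD and 11% for the GLM).

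A reader might also infer that the Day 126 comparison is biased under either branch once dropout relates to response. It is not: some difference between arms in loss or mechanism is needed. Nor does the evidence require a parametric primary analysis at every level of missingness, which at 18 to 36 per group is a trade-off against the rank and exact tests.

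**What to change.** **Above 20%, quantitative endpoints.** Take the Day 126 contrast from the repeated-measures likelihood already cited: log10 values at Days 0, 14 and 126, arm-by-visit and prior-regimen terms, and the censored version where values lie at an assay limit.

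**Above 20%, response rates at Day 126.** Bring in the Day 14 value by multiple imputation or inverse-probability weighting. Adding it as a regression covariate would condition the arm effect on a post-boost response. Specify a penalised or exact fit when an arm is all responders.

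**At or below 20%.** Keep the rank and exact complete-case tests, delete the clause on MCAR violations, report missingness by arm, and run the repeated-measures model as a sensitivity analysis.

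**Counting.** State that the 20% is counted per endpoint and timepoint.

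**Cost.** SAP wording and modest programming. The downside is reliance on a log-scale parametric model in the above-20% branch, at group sizes where the plan itself warns that such inference is limited.
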